7.3.2 Preparation of durvalumab doses for administration with an IV bag

The dose of durvalumab for administration must be prepared by the Investigator's or site's designated IP manager using aseptic technique. Total time from needle puncture of the durvalumab (MEDI4736) vial to the start of administration should not exceed:

- 24 hours at 2°C to 8°C (36°F to 46°F)
- 4 hours at room temperature

If the final product is stored at both refrigerated and ambient temperatures, the total time must not exceed 24 hrs

A dose of 1500 mg (for patients >30 kg in weight) will be administered using an IV bag containing 0.9% (w/v) saline or 5% (w/v) dextrose, with a final durvalumab concentration ranging from 1 to 15 mg/mL, and delivered through an IV administration set with a 0.2- or 0.22- μ m filter. Add 30.0 mL (i.e. 1500 mg) of durvalumab (i.e., 1500 mg of durvalumab) to the IV bag. The IV bag size should be selected such that the final concentration is within 1 to 15 mg/mL. Mix the bag by gently inverting to ensure homogeneity of the dose in the bag.

If patient weight falls to ≤ 30 kg weight-based dosing at 20 mg/kg will be administered using an IV bag size selected such that the final concentration is within 1 to 15 mg/mL.

Standard infusion time is 1 hour, however if there are interruptions, In the event that there are interruptions during infusion, the total allowed infusion time should not exceed 8 hours at room temperature.

Do not co-administer other drugs through the same infusion line.

[figure not shown]
The IV line will be flushed with a volume of IV diluent equal to the priming volume of the infusion set used after the contents of the IV bag are fully administered or

complete the infusion according to institutional policy to ensure the full dose is administered.

The IV line will be flushed according to local practices to ensure the full dose is administered. Infusion time does not include the final flush time.

If either preparation time or infusion time exceeds the time limits a new dose must be prepared from new vials. Durvalumab does not contain preservatives, and any unused portion must be discarded.

Figure 1. Durvalumab Dosing Schedule

7.4 Dose-limiting toxicities (DLTs)

A DLT is defined as the occurrence of an adverse event (AE) that is at least possibly related to the investigational product (IP) or investigational regimen (IR), with two exceptions: any grade of vitiligo or alopecia will not qualify as a DLT. AEs that are at least possibly related to durvalumab- and/or tremelimumab-containing regimens shall be assessed as DLTs if they meet any of the following criteria:

Hematologic toxicity:

- Grade ≥ 3 neutropenia complicated by fever $>38.3^{\circ}\text{C}$
- Grade 4 neutropenia (lasting more than 7 days)
- Grade ≥ 3 thrombocytopenia with significant bleeding
- Grade 4 thrombocytopenia (regardless of duration)
- Grade 4 anemia (regardless of duration)

Non-hematologic toxicity:

- Any Grade 4 non-immune-mediated AE
- Any Grade 4 immune-mediated AE, excluding endocrinopathies
- Any Grade 3 non-immune mediated AE that does not resolve to \leq Grade 1 or baseline within 30 days with optimal medical management
- Any Grade 3 immune-mediated AE – excluding diarrhea/colitis, pneumonitis, hepatitis, rash, neurotoxicity, myocarditis, myositis/polymyositis, endocrinopathies and nephritis – that does not resolve to \leq Grade 1 or baseline within 30 days after onset of the event despite optimal medical management including systemic corticosteroids

- Grade 3 diarrhea or colitis that does not resolve to \leq Grade 1 within 14 days [both immune- and non-immune-mediated indicated here; the same is the case if not specified in remaining bullet points below]
- Grade 3 non-infectious pneumonitis
- Grade 2 noninfectious pneumonitis that does not resolve to \leq Grade 1 within 3 days of the initiation of maximal supportive care
- Aspartate aminotransferase (AST) or alanine aminotransferase (ALT) $\geq 3 \times$ ULN with concurrent increase in total bilirubin (TBL) $\geq 2 \times$ ULN without evidence of cholestasis or alternative explanations (e.g., viral hepatitis, disease progression in the liver; i.e., “Hy’s Law”)
- ALT or AST $> 8 \times$ ULN or TBL $> 5 \times$ ULN
- Grade 3 immune-mediated rash that does not resolve to \leq Grade 1 or baseline within 30 days
- Grade 2 rash covering $> 30\%$ BSA that does not resolve to \leq Grade 1 or baseline within 30 days
- Any grade of immune-mediated rash with bullous formation
- Grade 3 immune-mediated neurotoxicity (excluding Guillain-Barre and myasthenia gravis) that does not resolve to \leq Grade 1 within 30 days
- Grade 2 or 3 immune-mediated peripheral neuromotor syndrome (such as Guillain-Barre and myasthenia gravis) that does not resolve to \leq Grade 1 within 30 days or that exhibits signs of respiratory insufficiency or autonomic instability
- Grade 3 immune-mediated myocarditis
- Any symptomatic immune-mediated myocarditis that does not become asymptomatic within 3 days of initiating optimal medical management including systemic corticosteroids
- Grade 2 or 3 immune-mediated myositis/polymyositis that does not resolve to Grade ≤ 1 within 30 days of initiating optimal medical management including systemic corticosteroids or that exhibits signs of respiratory insufficiency regardless of optimal medical management
- Immune-mediated increase in creatinine $> 3 \times$ ULN, or $> 3 \times$ baseline for patients with a baseline creatinine elevated above ULN

The period for evaluating DLTs will be from the time of first administration of durvalumab until the complete resolution of the treatment-related toxicity.

7.4.1 Management of toxicity

The following general guidance should be followed for management of toxicities:

1. Treat each of the toxicities with maximum supportive care (including holding the agent suspected of causing the toxicity where required).
2. If the symptoms promptly resolve with supportive care, consideration should be given to continuing study drug along with appropriate continuing

supportive care. If medically appropriate, dose modifications are permitted (see below).

3. All dose modifications should be documented with clear reasoning and documentation of the approach taken.

In addition, there are certain circumstances in which study drug should be permanently discontinued (see Appendix 3). Following the first infusion of study drug, subsequent administration of study drug can be modified based on toxicities observed as described in Appendix 3. All toxicities will be graded according to NCI CTCAE Version 5.0.

Dose reductions are not permitted for durvalumab.

Guidelines for the management of immune-mediated reactions, infusion-related reactions, and non-immune-mediated reactions for durvalumab are provided in the Toxicity Management Guidelines (TMGs) (see Appendix 3).

Dose modifications will not be required for AEs that are clearly not attributed to study drug (such as an accident) or for laboratory abnormalities that are not deemed to be clinically significant. Dosing may continue despite concurrent vitiligo of any AE grade. Based on the mechanism of action of Durvalumab leading to T cell activation and proliferation, there is the possibility of observing irAEs during the conduct of this study. Potential irAEs may be similar to those seen with the use of ipilimumab and nivolumab including immune-mediated enterocolitis, dermatitis, hepatitis, and endocrinopathies (Brahmer et al 2010, Hodi et al 2010). Patients should be monitored for signs and symptoms of irAEs. In the absence of an alternate aetiology (eg, infection or PD) signs or symptoms of enterocolitis, dermatitis, hepatitis, and endocrinopathy should be considered to be immune-related.

- Management of irAEs may require administration of immunosuppressive medications (and/or hormone replacement therapy for endocrinopathies). Resolution of irAEs managed in this manner in the timeframes specified is acceptable.
- Pneumonitis may be immune-related or as a result of late toxicity to radiotherapy. Either way study drug modifications detailed in this table should be followed.

AE Adverse event; irAE Immune-related adverse event; ULN Upper limit of normal.

7.4.2 Infusion-related reaction

In the event of a \leq Grade 2 infusion-related reaction, the infusion rate of study drug may be decreased by 50% or interrupted until resolution of the event (up to 4 hours) and re-initiated at 50% of the initial rate until completion of the infusion. For patients with a \leq Grade 2 infusion-related reaction, subsequent infusions may be administered at 50% of the initial rate. Acetaminophen and/or an antihistamine (eg, diphenhydramine) or equivalent medications per institutional standard may be administered at the discretion of the investigator. If the infusion-related reaction is \geq Grade 3 or higher in severity, study drug will be discontinued. As with any antibody, allergic reactions to dose administration are possible. Appropriate drugs and medical equipment to treat acute anaphylactic reactions must be immediately available, and study personnel must be trained to recognize and treat anaphylaxis. The study site must have immediate access to emergency resuscitation teams and equipment in addition to the ability to admit patients to an intensive care unit if necessary.

7.4.3 Pneumonitis

Pneumonitis has been reported in association with use of anti-PD-L1/anti-PD-1 antibodies (Brahmer et al 2012). It is also seen in 5% to 15% of patients irradiated for breast, lung, and mediastinal tumours. The risk of developing radiation pneumonitis is directly related to the volume of irradiated lung, the amount of radiation given, and the use of concurrent chemotherapy. Additional risk factors include co-morbid lung disease, poor baseline pulmonary function testing, and low performance status. Symptoms of radiation pneumonitis, including low-grade fever, congestion, dry cough, pleuritic chest pain, and a sensation of chest fullness, usually develop 1 to 3 months after completion of radiation therapy. Diagnosis is difficult, often complicated by co-morbid conditions and radiation injury to adjacent structures (eg, oesophagus, pericardium). Prednisone, in dosages of at least 50 to 60 mg per day for 1 week followed by an extended taper, has been shown to abate symptoms and improve lung function. Bronchodilators and supplemental oxygen may be necessary.

7.4.4 Hypersensitivity Reactions

Hypersensitivity reactions as well as infusion-related reactions have been reported with anti-PD-L1 and anti-PD-1 use (Brahmer et al 2012). As with the administration of any foreign protein and/or other biologic agents, reactions following the infusion of monoclonal antibodies can be caused by various mechanisms, including acute

anaphylactic (IgE-mediated) and anaphylactoid reactions against the monoclonal antibody, and serum sickness. Acute allergic reactions may occur, may be severe, and may result in death. Acute allergic reactions may include hypotension, dyspnoea, cyanosis, respiratory failure, urticaria, pruritis, angioedema, hypotonia, urticaria, arthralgia, bronchospasm, wheeze, cough, dizziness, fatigue, headache, hypertension, myalgia, vomiting and unresponsiveness.

7.4.5 Hepatic Function Abnormalities (Hepatotoxicity)

Increased transaminases have been reported during treatment with anti-PD-L1 (Brahmer et al 2012). Inflammatory hepatitis has been reported in 3% to 9% of patients treated with anti-CTLA-4 monoclonal antibodies (eg, ipilimumab). The clinical manifestations of ipilimumab-treated patients included general weakness, fatigue, nausea and/or mild fever and increased liver function tests such as AST, ALT, alkaline phosphatase, and/or total bilirubin. Cases where a patient shows AST or ALT ≥ 3 x ULN or total bilirubin ≥ 2 x ULN may need to be reported as SAEs.

7.5 Administration, dose delay, reduction or interruption for Regorafenib

Regorafenib tablets should be taken as follows:

- Once a day, approximately at the same time every day (the recommendation is to have at least a 20 hour interval between doses).
- With approximately 240 mL (8 fluid ounces) of water, after a light meal that contains less than 30% fat. Some examples of low-fat meals are:
 - Two slices of white toast with 1 tablespoon of low-fat margarine and 1 tablespoon of jelly and 8 ounces (240 mL) of skim milk (approximately 319 calories and 8.2 g of fat).
 - One cup of cereal (i.e. Special K), 8 ounces (240 mL) of skim milk, one piece of toast with jam (no butter or marmalade), apple juice and one cup of coffee or tea (2 g fat, 17 g protein, 93 g of carbohydrate, 520 calories).
- Tablets must not be chewed
- If a dose of regorafenib is missed, the missed dose should be skipped (vomited tablets cannot be made up), and the next dose should be taken at the regular time. The subsequent dose of regorafenib should not be doubled. The Investigator should be informed if the dose of regorafenib taken exceeded the scheduled dose.

7.5.1 Regorafenib Dose Levels

Dose Level	Daily Dose	Daily Dose	Daily Dose
Dose level patient is currently receiving	90 mg	60 mg	30 mg
Dose level -1	60 mg	30 mg	Not permitted*
Dose level -2	30 mg	Not permitted*	Not permitted*

* If a dose reduction is required to manage a regorafenib-related AE, then regorafenib must be discontinued.

Recommended dose modification for toxicities except hand-foot-skin reaction, hypertension and ALT/AST/bilirubin			
NCI-CTCAE v5.0 ^a	Dose interruption	Dose Modification ^b	Dose for Subsequent Cycles
Grade 0-2	Treat on time	No change	
Grade 3	Delay until ≤ Grade 2 ^c	Reduce by 1 dose level	If toxicity remains < Grade 2, dose re-escalation can be considered at the discretion of the treating investigator. If dose is re-escalated and toxicity (Grade 3) recurs, institute permanent dose reduction.
Grade 4	Delay until ≤ Grade 2 ^c	Reduce by 1 dose level. Permanent discontinuation can be considered at treating investigator's discretion.	

a. NCI-CTCAE = National Cancer Institute - Common Terminology Criteria for Adverse Events, version 5.0
b. Excludes alopecia, non-refractory nausea/vomiting, lymphocyte count decreased, non-refractory hypersensitivity and nonclinical and asymptomatic laboratory abnormalities.
c. If no recovery after a 4 week delay*, treatment should be permanently discontinued unless subject is deriving clinical benefit.

If greater than 2 dose level reductions are required, regorafenib will be discontinued and the rest of the study follow up may be continued. The following tables outline dose adjustments for toxicities related to regorafenib except hand-foot skin reaction, hypertension and liver function test abnormalities.

The table above outlines dose adjustments for hematologic and non-hematologic toxicities related to regorafenib except PPES and hypertension. In addition to these recommended dose modifications, subjects who develop diarrhea, mucositis, anorexia or other events predisposing to fluid loss or inadequate fluid intake should be carefully monitored and rehydrated as clinically necessary. This is in order to minimize the risk of postural hypotension and renal failure.

Regorafenib Dose Modification Guidance, Non-Immune Toxicities: Hand-Foot Skin Reaction Related to Regorafenib Only

CTCAE v5.0 Grade	Occurrence	Recommended Management
G1	Any	
 Maintain dose level and immediately institute supportive measures for symptomatic relief.
G2	1 st occurrence	
 Consider decreasing dose by 1 dose level and immediately institute supportive measures. If no improvement, interrupt therapy for a minimum of 7 days, until toxicity resolves to G0-1.^{a, b}
	No improvement within 7 days or 2 nd occurrence	
 Interrupt therapy until toxicity resolves to G0-1.^b When resuming treatment, treat at reduced dose level.^a
	3 rd occurrence	
 Interrupt therapy until toxicity resolves to G0-1.^b When resuming treatment, decrease dose by 1 dose level.
	4 th occurrence	
 Discontinue permanently.
G3	1 st occurrence	
 Institute supportive measures immediately. Interrupt therapy for a minimum of 7 days until toxicity resolves to G0-1. When resuming treatment, decrease dose by 1 dose level.
	2 nd occurrence	
 Institute supportive measures immediately. Interrupt therapy for a minimum of 7 days until toxicity resolves to G0-1. When resuming treatment, decrease dose by 1 additional dose level.
	3 rd occurrence	Discontinue permanently.

Abbreviations: CTCAE=common terminology criteria for adverse events; G=Grade If reductions are required resulting in a daily dose of less than 30 mg of regorafenib, regorafenib will be permanently discontinued. Footnotes: a) If toxicity returns to G0-1 after dose reduction, dose re-escalation is not permitted. b) If there is no recovery after a 4-week delay (28 days) (including the 1 week drug holiday), treatment with regorafenib will be discontinued permanently.
		

Regorafenib Dose Modification Guidance, Non-Immune Toxicities: Hypertension

CTCAE v5.0 Grade	Suggested regorafenib dose modification
Specific guidance for Hypertension	
G1	
 No change. Consider increased BP monitoring.
G2	
 If symptomatic, hold until symptoms resolve. At restart, continue at the same dose level.
G3	
 Hold until diastolic BP < 100 mm Hg, and if symptomatic, until symptoms resolve. At restart, continue at the same dose level. If BP is not controlled with the addition of new or more intensive therapy, reduce by 1 dose level. If G3 hypertension recurs despite dose reduction and antihypertensive therapy, reduce another dose level.
G4	
 Discontinue permanently.

Abbreviations: BP=blood pressure; CTCAE=common terminology criteria for adverse events; G=Grade; Hg=mercury
 
If reductions are required resulting in a daily dose of less than 30 mg of regorafenib, regorafenib will be permanently discontinued. If BP remains controlled for at least one full cycle, dose re-escalation is permitted at the Investigator's discretion. Patients requiring a delay of > 4 weeks (28 days) (including the 1 week drug holiday) should discontinue regorafenib treatment. However, continuation of regorafenib may be considered if, in the Investigator's opinion, the patient may continue to benefit from the regorafenib treatment, and after consultation with the Medical Monitor.
	

Regorafenib Dose Modification Guidance, Non-Immune Toxicities: Liver Function Test Abnormalities^a

Increases in AST/ALT and/or bilirubin	1 st occurrence	Restart	Recurrence
AST and/or ALT ≤ to 5 x ULN, with normal AST and/or ALT at baseline	Continue dosing , with weekly monitoring of liver function until transaminases return to < 3 x ULN (< or equal to G1) or baseline.		
AST and/or ALT > 5 x ULN	Interrupt dosing , with weekly monitoring of liver function until transaminases return to < 3 x ULN or baseline.	If the potential to reinitiate regorafenib is considered to outweigh the risk of hepatotoxicity: reduce 1 dose level and measure serum transaminases weekly for at least 4 weeks.	Discontinue permanently
AST and/or ALT > 20 x ULN	Discontinue permanently and measure serum transaminases weekly until resolution.		

AST and/or ALT > 3 x ULN with concurrent total bilirubin > 2 x ULN	Discontinue permanently and measure serum transaminases weekly until resolution. Exception: participants with Gilbert's syndrome who develop elevated transaminases should be managed as per the above outlined recommendations for the respective observed elevation of ALT and/or AST.		

Abbreviations: ALT=alanine aminotransferase; AST=aspartate aminotransferase; ULN=upper limit of normal; G=Grade
 
If reductions are required resulting in a daily dose of less than 30 mg of regorafenib, regorafenib will be permanently discontinued.
 
Footnote:
 
a) If all values remain stable for 2 full cycles, dose re-escalation may be considered at the discretion of the Investigator. After re-escalation AST, ALT, bilirubin should be checked 2x/week for 2 weeks, followed by weekly assessments for at least 4 weeks.
			

7.6 Method of Assigning Patients to Treatment Groups

Randomization, according to a 1:1 ratio, will be performed using centre as stratification variable.

7.6.1 Method of collection of Patients Data

Data collection will be granted electronically through the internet (remote data entry, RDE) to data managers and clinical investigators at each clinical site using a safe internet based procedure, providing the best and most secure on line data entry process and a daily backup of all collected data. RDE will be done via connection only after the identification via individual user name and password.

For each clinical site, individual user names and passwords will be granted to the principal investigator and to qualified delegated staff members by GISCAD upon reception of a delegation log form dated and signed by all the staff members involved in the trial and the documentation of the affirmative decision of the IEC that the clinical trial has been reviewed and may be conducted at the institution site within the constraints set by the IEC, the institution, GCP, and the applicable regulatory requirements (ICH E6).

7.7 Prior and Concomitant Therapies

All relevant medications administered within 4 weeks prior to the randomization visit are to be recorded as prior medications; medications administered from the time of signing the ICF are to be recorded as concomitant medications. Both prior and concomitant medications are to be documented in the eCRF.

7.8 Prohibited Therapies

Prohibited medication/class of drug:	Usage:
Any investigational anticancer therapy other than those under investigation in this study	Should not be given concomitantly whilst the patient is on study treatment
mAbs against CTLA-4, PD-1, or PD-L1 other than those under investigation in this study	Should not be given concomitantly whilst the patient is on study treatment
Any concurrent chemotherapy, radiotherapy, immunotherapy, or biologic or hormonal therapy for cancer treatment other than those under investigation in this study	Should not be given concomitantly whilst the patient is on study treatment. (Concurrent use of hormones for non-cancer-related conditions [e.g., insulin for diabetes and hormone replacement therapy] is acceptable. Local treatment of isolated lesions, excluding target lesions, for palliative intent is acceptable [e.g., by local surgery or radiotherapy])
Immunosuppressive medications including, but not limited to, systemic corticosteroids at doses exceeding 10 mg/day of prednisone or equivalent, methotrexate, azathioprine, and tumor necrosis factor- α blockers	
Should not be given concomitantly, or used for premedication prior to the I-O infusions. The following are allowed exceptions:
 
 • Use of immunosuppressive medications for the management of IP-related AEs. • Use in patients with contrast allergies. • Use of inhaled, topical, and intranasal corticosteroids is permitted. 
A temporary period of steroids will be allowed if clinically indicated and considered to be essential for the management of non-immunotherapy related events experienced by the patient (e.g., chronic obstructive pulmonary disease, radiation, nausea, etc.).

Live attenuated vaccines	Should not be given through 30 days after the last dose of IP (including SoC)
Herbal and natural remedies which may have immune-modulating effects	Should not be given concomitantly unless agreed by the sponsor

Patients in any arm who take prohibited medications will be considered protocol violators and thus excluded from the present study.

7.9 Treatment Compliance

The details of each administration of study treatment will be documented in the eCRF.

8 STUDY VISITS AND PROCEDURES

The timing of all assessments and procedures is detailed in Section 8.1; details of procedures and assessments to be done are provided in Section 8.2; Schedules of Events for pre-randomization, treatment periods and long term follow-up are provided in Table 1, Table 2 and Table 3.

Any procedures other than those indicated will be considered SoC of the facility, and not part of the study. Data from any CEA/CA 19-9 analyses or CT scans done as part of SoC procedures should be collected and recorded in the eCRF.

For all treatment arms

Tumor efficacy (RECIST) assessment dates are not affected by dose delays and remain as originally scheduled, as they are based on the date of randomization (not the date of therapy).

All other scheduled assessments must be performed relative to the start of the dosing cycle such that all laboratory procedures, etc. required for dosing should be performed within 3 days prior to dosing.

For durvalumab + regorafenib combination arms

Patients may delay dosing under certain circumstances.

- Dosing may be delayed per Toxicity Management Guidelines, due to either an immune or a non-immune-related AE.
- If dosing must be delayed for reasons other than treatment-related toxicity, dosing will resume as soon as feasible
- Dosing_intervals of subsequent cycles may be shortened as clinically feasible in order to gradually align treatment cycles with the schedule of tumor efficacy (RECIST). Subsequent time between 2 consecutive doses cannot be less than 22 days, based on the half-lives of durvalumab (see current Investigator Brochure for durvalumab).

Standard of Care Arm:

Patients may delay and subsequently resume dosing per local standard clinical practice.

If dosing must be delayed for reasons other than treatment-related toxicity, dosing will occur as soon as feasible.

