2.11 Rationale for Regorafenib dose in combination with Durvalumab

Regorafenib will be administered at a dose of 90 mg orally, once daily (q.d.) for 3 weeks in a 4-week cycle. Durvalumab will be administered intravenously (i.v.) at a dose of 1500 mg every 4 weeks (Q4W).

The dose of regorafenib is lower than the dose currently approved in CRC and other indications. The selection of this dose is based on the recently published REGONIVO trial as well as data from other ongoing trials, as explained below. REGONIVO was a phase Ib trial that enrolled 50 patients with pre-treated metastatic gastric and colorectal cancer. Patients received (during the dose expansion phase), 80-120 mg of regorafenib in combination with nivolumab. The 80 mg dose had a manageable safety profile and encouraging antitumor activity (objective tumor response 40%) in patients with heavily pretreated disease. Based on these promising results, the Rego-Nivo combination is being tested in a number of ongoing clinical trials, including an industry-sponsored phase II trial in patients with mismatch repair-proficient advanced colorectal cancer and two phase II trials in unresectable HCC.

Based on data from the combination of regorafenib and nivolumab in the REGONIVO trial, the combination of regorafenib and pembrolizumab in an ongoing HCC trial, as well as ongoing data from a phase II regorafenib + nivolumab trial in colorectal cancer (Bayer - data on file), a few observations are noted:

- A starting dose of 120 mg of regorafenib cannot be sustained in the majority of patients, predominantly due to rash.
- A starting dose of 80 mg is more tolerable and certain patients can maintain therapy at this dose as well as escalate to 120 mg; however approximately 25% of Western patients require further dose reduction.

It is therefore not clear whether additional efficacy beyond that seen with an 80 mg starting dose could be observed, this suggests that the optimal dose of regorafenib in combination with a PD-(L)1 inhibitor may lie between 80 and 120 mg.

Since there is no pharmacodynamic marker for the regorafenib activity in combination with a PD-(L)1 inhibitor, empirically one can conclude that an intermediate dose closer to 80 mg would have a lower likelihood of eliciting toxicity. However, concerns regarding unrealized efficacy may remain. Conversely, a dose closer to 120 mg may elicit toxicity, leading to higher rates of discontinuation.

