7.1 Treatment Administered

Patients randomized and assigned to experimental arm will receive Regorafenib + durvalumab. Treatment will begin only after the patient has been randomized to the Treatment Group. Regorafenib 90 mg will be administered orally once daily for the first 21 days of each 28-day cycle, up to 1 year. Durvalumab (1500mg q4W IV infusion) will be administered every four weeks up to 1 year.

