8.1 Study Visits

8.1.1 Screening

Screening, to verify inclusion and exclusion criteria, will include:

1. obtaining written informed consent from patient or legally authorised representative (Section 8.2.1.1)
2. Review of eligibility criteria
3. documentation of demographics and medical history (Section 8.2.1.2)
4. Complete physical examination (Section 8.2.2.1)
5. vital signs (Section 8.2.2.2)
6. ECOG performance status (Section 8.2.2.3)
7. 12-lead electrocardiogram (ECG; Section 8.2.2.4)
8. clinical chemistry, coagulation profile and haematology (Section 8.2.2.45)
9. CEA and CA 19-9 analysis, backup plasma sample (Section 8.2.3.2)
10. pregnancy test (serum or urine) for female patients of child-bearing potential (Section 8.2.1.3); patients with positive results will be discontinued from the study with no further study procedures performed
11. CT/MRI/PET scan of chest and abdomen with tumor measurement and evaluation by RECIST 1.1 criteria (Section 8.2.3.3)
12. documentation of prior and concomitant medications (Section 7.7)
13. Histological confirmation

Patients who meet the inclusion/exclusion criteria (Section 6) will be randomized to one of the following:

1. Treatment arm (Regorafenib + Durvalumab)
2. Control arm

8.1.2 Treatment Phase: Table 2 and 3.

Patients allocated to regorafenib + durvalumab arm will undergo visits every week for the first cycle, every 2 weeks for the second cycle, and monthly thereafter.

Patients allocated to the control group will undergo visits every 12 weeks.

If at any time a relapse is confirmed, the patient will discontinue treatment. Patients in the control arm will be offered to crossover to regorafenib plus durvalumab.

All visits have a window of ± 7 days.

- Patients allocated to Treatment arms will undergo the following procedures and assessments:

At each visit:

1. Limited physical examination
 2. vital signs
 3. ECOG performance status
 4. Weight
 5. Clinical chemistry and haematology (CBC + differential platelet count; creatinine; total bilirubin; AST; ALT; alkaline phosphatase; LDH; albumin; glucose; potassium; sodium; calcium)
 6. administration of therapy (regorafenib plus durvalumab at Day 1 of every cycle)
 7. documentation of AEs/SAEs
 8. documentation of concomitant medications and procedures (at Day 1 of every cycle)
 9. CEA and CA19-9 analysis and CT/MRI/PET scan as per baseline assessment: every 12 weeks. From day 1 (\pm 7 days).

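### Combination cycles may be shortened to 22 days on durvalumab half-life alone, which can cut the 7-day regorafenib rest to as little as 1 day

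*Combined protocol and SAP*

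**What the plan says.** Section 8, under its heading for the durvalumab plus regorafenib arm, deals with delayed dosing. Toxicity is one permitted reason: "Dosing may be delayed per Toxicity Management Guidelines, due to either an immune or a non-immune-related AE". Delays for other reasons are also covered. Afterwards, the dosing intervals of later cycles "may be shortened as clinically feasible in order to gradually align treatment cycles with the schedule of tumor efficacy (RECIST"). The only floor is "Subsequent time between 2 consecutive doses cannot be less than 22 days, based on the half-lives of durvalumab".

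The regorafenib schedule is in Section 7.1: "Regorafenib 90 mg will be administered orally once daily for the first 21 days of each 28-day cycle, up to 1 year". Section 2.11 gives the same three-weeks-in-four pattern in the dose rationale. The toxicity rules in Section 7.5.1 count the off-week as part of the regimen, for example "If there is no recovery after a 4-week delay (28 days) (including the 1 week drug holiday") in the hand-foot skin reaction footnote. The hypertension note uses the same convention.

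The two drugs are tied together in Section 8.1.2: "administration of therapy (regorafenib plus durvalumab at Day 1 of every cycle"). Table 2 marks both drugs in the same Day 1 columns. Section 8.1.2 also gives every visit a window of ±7 days.

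Section 8 separately fixes the scan calendar by randomization date; tumour "assessment dates are not affected by dose delays and remain as originally scheduled". The notes to the schedule tables set scans every 12 weeks, ±1 week, in the first year.

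**The concern.** The 22-day floor is reasoned from one drug and applied to cycles of two. Because regorafenib is taken daily, an interval between consecutive doses can only describe infusions. Yet the permission is to shorten cycles, and a cycle starts both drugs. Sections 7.1, 7.2 and 7.5 and Appendix 3 do not say what happens to the tablets or the off-week in a shortened cycle.

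What is at stake is patient safety, over a limited period. Delays may follow toxicity, so compression can fall on someone who has recently had some. The resumption rules in Section 7.5.1 control when regorafenib restarts. None sets a minimum rest in the cycles that come after.

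**Working it through.** The plan states no figure on this point, so there is nothing to reproduce. The check is cycle arithmetic.

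**Inputs.** Regorafenib 90 mg on 21 days of a 28-day cycle (Section 7.1); minimum interval 22 days (Section 8); shared Day 1 and ±7-day visit window (Section 8.1.2); scans every 12 weeks ±1 week from randomization (schedule notes); dose reductions (Section 7.5.1). *Assumption:* an illustrative delay of 14 days with both drugs paused.

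**1. Rest in a cycle of length L, keeping 21 dosing days.** Rest = L − 21; average dose = 90 × 21 / L.
- L = 28: 7 rest days, 67.5 mg/day (planned).
- L = 26: 5 rest days, 72.7 mg/day.
- L = 24: 3 rest days, 78.8 mg/day.
- L = 22: 1 rest day, 85.9 mg/day; 28/22 = 1.27, so 27% above plan within that cycle.

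The alternatives at 22 days are 22 − 7 = 15 dosing days, against the 21-day rule, or a regorafenib start that differs from the infusion day, against the shared Day 1. Each choice departs from something written.

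**2. Fastest permitted recovery of 14 days.** Each cycle can give back at most 28 − 22 = 6 days; 14/6 = 2.3, so three cycles, for example 22, 22 and 26 days (rests 1, 1, 5). First to last tablet: 21 + 1 + 21 + 1 + 21 = 65 days containing 63 dosing days. Planned: 21 + 7 + 21 + 7 + 21 = 77 days.

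**3. Recovery using the scan window.** The ±7 days absorb half of the delay, leaving 14 − 7 = 7 days to recover. Over three cycles: 26 + 26 + 25 = 77 = 84 − 7, with rests of 5, 5 and 4 days and 63 dosing days in 21 + 5 + 21 + 5 + 21 = 73. A delay of 7 days or less needs no shortening. Nor does one of 28 days, because 12 weeks = 84 = 3 × 28 days and dosing is back on the scan grid.

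**4. Cumulative dose.** Counting the 14 drug-free days, the fastest case gives 90 × 63 / (14 + 70) = 67.5 mg/day, exactly as planned. The slower case gives 90 × 63 / (14 + 77) = 62.3 mg/day.

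**5. After a one-level reduction.** 60 × 21 / 22 = 57.3 mg/day, below the 67.5 planned at full dose. The rest is still 1 day.

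**6. Visit window.** A Day 1 visit 7 days early gives 28 − 7 = 21 days. The 22-day floor blocks that for infusions, but nothing blocks it for tablets.

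**The case against.** The best defence is that the floor concerns infusions only and regorafenib simply keeps its own 28-day clock, which no text changes. The protocol already lets the drugs part company: Section 7.2 leaves it to the investigator which drug to reduce or withhold, and Section 7.5.1 interrupts regorafenib alone. On this view the shared Day 1 is a default in a visit checklist. That is a sensible reading and the one the fix would write down. But a site has to infer it against the wording of Section 8.1.2, and Section 8 speaks of aligning treatment cycles.

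The second defence concerns size, and it largely stands. Shortening is optional, gradual and subject to feasibility. Section 7.5.1 requires a lower dose after Grade 3 toxicity in the general table, after Grade 3 hand-foot reaction, and on restart after AST/ALT above 5 × ULN. Grade 4 in the general table means reduction or discontinuation. Patients still on 90 mg are mainly those with durvalumab-only toxicity, a hypertension hold (restarted at the same dose), a re-escalated dose, or a delay unrelated to toxicity. Laboratory tests within 3 days before dosing, adverse event review at visits and the interruption rules still apply in shortened cycles.

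A reader might infer that the rule causes overdose, or that patients recovering from regorafenib toxicity typically receive 27% more drug. The documents do not support either. Under the stated assumption cumulative dose does not exceed plan, and the 27% is a per-cycle upper bound at 90 mg. Nor does any text say that a shorter rest is unsafe; the harm is inferred from losing a rest that the regimen includes.

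**Conclusion.** The inconsistency is real and minor. Section 8 states a cycle-shortening limit that fits only one of the two drugs, and followed literally with a shared Day 1 it can reduce the regorafenib rest from 7 days to 1. The more likely outcome, if a site uses the scan window, is a rest of 4 to 5 days for three cycles after a 14-day delay.

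This rests on three assumptions: the site keeps 21 tablet days and a common Day 1, both drugs were paused during the delay, and the delay was 14 days.

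The shortening is not needed for efficacy assessment, because scan dates do not move with dosing. A reader might also infer damage to the primary comparison. Nothing here affects sample size, the DFS definition or the log-rank test.

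**What to change.** Add to Section 8: *The 22-day minimum applies to durvalumab infusions only; a new regorafenib course may not start until at least 7 regorafenib-free days have followed the previous 21-day course.* State in Section 8.1.2 that neither the ±7-day visit window nor the shared Day 1 overrides this rest.

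A simpler alternative is not to shorten combination cycles below 28 days for realignment, and to say that the visit window does not permit an earlier regorafenib start.

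The cost is two or three sentences and some logistics. Under the first option, tablet starts drift from infusion days. With infusions at days 0, 26, 52 and 77 and tablets at 0, 28, 56 and 84, the lag is 2, 4 and then 7 days. At the fastest pace (infusions at 0, 22, 44 and 70) it is 6, 12 and then 14 days. The gap stays until one drug is held back, and may need separate dispensing and safety bloods. Under the second option Day 1 stays shared, but after a delay some scan and CEA visits fall between dosing visits. Neither option changes sample size, endpoint or scan dates.
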